10.5 SAFETY ANALYSES

All safety analyses and summaries will be conducted using the Safety Population. Unless otherwise stated.

Extent of Exposure

The duration of treatment will be summarized.

CONFIDENTIAL AND PROPRIETARY

This document contains information that is confidential and proprietary to Smith & Nephew PLC and Smith & Nephew, Inc. and is intended for use only by Smith & Nephew and its manufacturer. It shall not be reproduced or copied in whole or in part, nor shall the contents be disclosed by any means without prior written permission from Smith & Nephew, nor shall anyone make any use of it that is contrary to the expressed or implied wishes of Smith & Nephew.

| | |
|--|---|
| Study Protocol—Device |  |
| A Prospective, Multi-center, Post-Market Clinical Follow-Up Study to Evaluate the Safety and Effectiveness of ALLEVYN Gentle Border | Number: ALLEV.PMCF.2017.13 |
| | Version: 3.0 |
| | Date: 21 JUN 2019 |
| | Page: Page 52 of 90 |

Adverse Events

Adverse events will be coded and grouped by system organ class using the Dictionary for Medical Drug Regulatory Activities (MedDRA).

The number of subjects reporting: adverse events (AE), serious adverse events (SAE), adverse device effects (ADE), serious adverse device effects (SADE) and unanticipated serious adverse effects (USADE) will be summarized. In addition, AEs will be summarised by: severity; the relationship to the investigational device; outcome and duration of adverse events at trial discontinuation.

Further safety summaries may be defined in the SAP.

10.6 INTERIM ANALYSES

Not Applicable

11. SAMPLE SIZE JUSTIFICATION

The sample size determination for this study was based on a previous study (CE/046/ALF) demonstrating an absolute mean reduction in wound area from baseline to 28 days of 3cm² with a standard deviation of 5cm², in a range of moderate to highly exuding wound types. In order to show a statistically significant reduction in the mean wound area for this study, it was calculated that 26 subjects would achieve 83% power.

Unfortunately, several subjects were recruited into the current study with wounds smaller than 3cm², little to no exudate or chronic wounds of less than 6 weeks duration, meaning these wounds are not comparable to the previous study in terms of healing challenge. As a result, protocol modifications have been made to ensure a minimum wound size is included in the inclusion criteria as well as provide an opportunity to re-emphasise the challenging nature of wounds we are seeking to recruit with regards to level of exudate. With this in mind and accounting for the 10 patients enrolled in the study under protocol V2.0 (as at 19 June 2019), it is recommended we

CONFIDENTIAL AND PROPRIETARY

This document contains information that is confidential and proprietary to Smith & Nephew PLC and Smith & Nephew, Inc. and is intended for use only by Smith & Nephew and its manufacturer. It shall not be reproduced or copied in whole or in part, nor shall the contents be disclosed by any means without prior written permission from Smith & Nephew, nor shall anyone make any use of it that is contrary to the expressed or implied wishes of Smith & Nephew.

| | |
|--|---|
| Study Protocol—Device |  |
| A Prospective, Multi-center, Post-Market Clinical Follow-Up Study to Evaluate the Safety and Effectiveness of ALLEVYN Gentle Border | Number: ALLEV.PMCF.2017.13 |
| | Version: 3.0 |
| | Date: 21 JUN 2019 |
| | Page: Page 53 of 90 |

increase the total patient recruitment target to n = 35 patients to ensure we have captured a range of wounds of comparable healing challenge to the previous study.

Using the same assumptions, it can be calculated that 35 subjects would provide 93% power to show a statistically significant reduction in the mean wound area from baseline to 28 days. Analysis for this study will be conducted separately for patients that comply with V3.0 of the protocol and therefore the study is over-powered to allow for greater than 80% power in the V3.0 protocol population.

Allowing for a 15% lost to follow up rate as used previously, 40 subjects will be recruited into this study.

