10.2 ANALYSIS POPULATIONS

The following analysis populations will be used for this study:

- **Safety Population (SAF):** Including all subjects who enroll in the study and receive the study treatment. This population will be used for analysis of safety.
- **Modified Intention to Treat population (mITT):** following Intention to Treat principle including all subjects who are enrolled into the study and complete at least one post-baseline assessment. This population will be used for the primary analysis of the primary and secondary endpoints.

CONFIDENTIAL AND PROPRIETARY

This document contains information that is confidential and proprietary to Smith & Nephew PLC and Smith & Nephew, Inc. and is intended for use only by Smith & Nephew and its manufacturer. It shall not be reproduced or copied in whole or in part, nor shall the contents be disclosed by any means without prior written permission from Smith & Nephew, nor shall anyone make any use of it that is contrary to the expressed or implied wishes of Smith & Nephew.

| | |
|--|---|
| Study Protocol—Device |  |
| A Prospective, Multi-center, Post-Market Clinical Follow-Up Study to Evaluate the Safety and Effectiveness of ALLEVYN Gentle Border | Number: ALLEV.PMCF.2017.13 |
| | Version: 3.0 |
| | Date: 21 JUN 2019 |
| | Page: Page 49 of 90 |

- **Per-Protocol Population (PP):** including all subjects in the mITT, who have no significant protocol deviations and who meet the inclusion/exclusion criteria. This population will be used for a secondary analysis of the primary and secondary endpoints.

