10.4 EFFICACY ANALYSIS

10.4.1 Analysis of Primary Endpoint

The primary endpoint for this study is the absolute reduction in wound area from baseline to end of study.

The reference wound area will be summarised at each dressing change assessment and study visit. The absolute reduction in the reference wound area from baseline to each post-baseline study visit will also be summarised.

The absolute reduction in area will be analysed as the dependent variable in a repeated measures ANCOVA model. As a minimum the models will contain a term for visit and the following terms will be added to the model using a stepwise selection procedure with an F-value to attain a significance level of 0.1: centre, wound type, BMI and baseline area. The estimate LSMean reduction in area from baseline to all study visits will be presented with the associated 95% confidence intervals, with the estimate for the end of study visit (day 28±3) being used for analysis of the primary endpoint.

If the assumptions of ANCOVA are not met then a non-parametric analysis will be considered.

The primary analysis analysis of this endpoint is to be carried out using the mITT population. The same analysis will be carried out on the PP population as a secondary analysis.

CONFIDENTIAL AND PROPRIETARY

This document contains information that is confidential and proprietary to Smith & Nephew PLC and Smith & Nephew, Inc. and is intended for use only by Smith & Nephew and its manufacturer. It shall not be reproduced or copied in whole or in part, nor shall the contents be disclosed by any means without prior written permission from Smith & Nephew, nor shall anyone make any use of it that is contrary to the expressed or implied wishes of Smith & Nephew.

| | |
|--|---|
| Study Protocol—Device |  |
| A Prospective, Multi-center, Post-Market Clinical Follow-Up Study to Evaluate the Safety and Effectiveness of ALLEVYN Gentle Border | Number: ALLEV.PMCF.2017.13 |
| | Version: 3.0 |
| | Date: 21 JUN 2019 |
| | Page: Page 50 of 90 |

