10.4.2 Analysis of Secondary Endpoints

All secondary endpoints will be analysed using the mITT population as the primary analysis.

Wound Measurements

The reference wound volume and depth will be summarised at each dressing change assessment and study visit. The absolute reduction in the reference wound volume and depth from baseline to each visit will also be summarised.

The same analysis as the above repeated ANCOVA model is planned to be used to analyse absolute reduction in volume and depth (separately) from baseline to all post-baseline study visits. As well as the summaries of absolute reduction, the percentage reduction in area, volume and depth will also be summarised from baseline to all post-baseline study visits.

Cardiff Wound Impact Schedule (CWIS):

The CWIS consists of three domains: Social Life (CWIS-SL), Wellbeing (CWIS-WB), Physical Symptoms and Daily Living (CWIS-PSDL). For each domain a score from 0-100 is derived with higher scores being better.

Scores for each CWIS domain will be summarised at each study visit by wound type and overall. The increase in score from baseline to each study visit will also be summarised by wound type and overall.

A repeated measures ANCOVA model will be fit separately for each CWIS domain. In each case the domain score will be used as the dependent variable and as a minimum the model will contain a term for visit. The following extra terms will be added to the model using a stepwise selection procedure with an F-value to attain a significance level of 0.1: centre, wound type, BMI and baseline domain score. The estimate LSMean increase in domain score from baseline to all study visits will be presented with the associated 95% confidence intervals.

If the assumptions of ANCOVA are not met then a non-parametric analysis will be considered.

CONFIDENTIAL AND PROPRIETARY

This document contains information that is confidential and proprietary to Smith & Nephew PLC and Smith & Nephew, Inc. and is intended for use only by Smith & Nephew and its manufacturer. It shall not be reproduced or copied in whole or in part, nor shall the contents be disclosed by any means without prior written permission from Smith & Nephew, nor shall anyone make any use of it that is contrary to the expressed or implied wishes of Smith & Nephew.

| | |
|--|---|
| Study Protocol—Device |  |

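### Does the separate V3.0 analysis promised in Section 11 need a population definition and a recruitment floor before its power claim can stand?

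*Combined protocol and SAP*

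**What the plan says.** Section 11 bases the sample size on an earlier study with a mean area reduction of 3 cm² and an SD of 5 cm². It gives 83% power at 26 subjects and 93% at 35. The increase to 35 is made "accounting for the 10 patients enrolled in the study under protocol V2.0 (as at 19 June 2019"). The section then says "Analysis for this study will be conducted separately for patients that comply with V3.0 of the protocol and therefore the study is over-powered", with the purpose "to allow for greater than 80% power in the V3.0 protocol population". It closes: "Allowing for a 15% lost to follow up rate as used previously, 40 subjects will be recruited into this study".

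Section 10.2 defines three populations: safety, mITT and per-protocol (PP). PP is described as "including all subjects in the mITT, who have no significant protocol deviations and who meet the inclusion/exclusion criteria", with no version stated. For the primary endpoint, Section 10.4.1 says "The primary analysis analysis of this endpoint is to be carried out using the mITT population" and "The same analysis will be carried out on the PP population as a secondary analysis". Section 10.4.2 says "All secondary endpoints will be analysed using the mITT population as the primary analysis". None of these mentions a V3.0 set.

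Four other provisions bear on the point:

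- Section 7.2, criterion 5, requires a moderately to highly exuding wound of at least 3 cm². Section 21.1.4 lists this criterion as added in V3.0.
- Section 7.6 makes enrolment conditional on meeting every eligibility criterion.
- Section 7.8.1 withdraws and replaces subjects whose wound proves too small when traced at Visit 1.
- The opening of Section 10 calls itself a brief description and sends any changes to the SAP and the study report.

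**The concern.** Sections 10 and 11 of the same protocol do not match. Section 11 gained a V3.0 analysis in the amendment, but the population list in Section 10.2 did not. Two readings of the set are possible: subjects who meet the V3.0 criteria whenever they enrolled, or subjects enrolled under V3.0. PP does not settle the matter, because a V2.0 subject with a wound under 3 cm² could be counted in or out.

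The power statement also looks exposed. The set needs 24 evaluable subjects to exceed 80%, yet the only target is 40 recruits of any version. The count of ten V2.0 subjects is dated 19 June 2019, and Section 15 requires approval before an amendment is used at a site, so V2.0 enrolment could have continued. Section 7.8.1 replaces subjects for wound size only, not for low exudate or short duration. At stake would be an open-label, single-arm study whose V3.0 set is chosen after the data are seen and falls short of its stated power.

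**Working it through.** **Inputs.** Two-sided alpha 0.05 (Section 10.1). Mean 3 cm², SD 5 cm², so the standardised effect is 3/5 = 0.6 (Section 11). Loss 15%, 40 recruits, ten of them enrolled under V2.0 (Section 11).

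**Formula.** One-sample t-test of the mean reduction. Power = P(|T| > t₀.₉₇₅,ₙ₋₁), where T is noncentral t with n − 1 degrees of freedom and noncentrality 0.6√n.

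**Reproducing the plan.** At n = 26 the noncentrality is 0.6 × 5.099 = 3.06 and power is 83.65% (plan: 83%). At n = 35 it is 0.6 × 5.916 = 3.55 and power is 93.2% (plan: 93%). Both agree. The normal approximation gives 86.4% and 94.4%, so the plan used the two-sided t-test.

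**Threshold.** n = 23 gives 78.5%, n = 24 gives 80.4% and n = 25 gives 82.1%. The smallest evaluable number above 80% is 24.

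**What the plan implies.** Removing all ten V2.0 subjects from the 35 evaluable leaves 25, with 82.1% power. A stricter count also passes: 40 × 0.85 = 34 evaluable, and taking all ten from those leaves 24, with 80.4%.

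**How far it can slip.** Evaluable = (40 − number outside the set) × 0.85.

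| Outside the set | Evaluable | Power at the whole numbers on either side |
|---|---|---|
| 10 | 25.5 | 82.1% to 83.6% |
| 11 | 24.65 | 80.4% to 82.1% |
| 12 | 23.8 | 78.5% to 80.4% |
| 13 | 22.95 | 76.5% to 78.5% |

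Twelve outside sits on the line and thirteen falls below it. The documents report ten.

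**If the set is defined by baseline criteria.** V2.0 subjects who meet the V3.0 criteria then stay in. Section 11 says only that several did not fit, so assume 3 to 7 of the ten. With 7 outside, 33 × 0.85 = 28.05, and n = 28 gives 86.4%. With 3 outside, 37 × 0.85 = 31.45, and n = 31 gives 89.8%.

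**Loss rate and the analysis set.** The 15% deduction treats every lost subject as contributing nothing. Under Section 10.2 one post-baseline assessment keeps a subject in mITT, and Section 10.4.1 fits a repeated-measures model over all visits. If a V3.0 set were built on mITT and nobody left it, 24 would remain with as many as 40 − 24 = 16 outside. Early dropouts carry less information on Day 28, so the true limit lies between 11 and 16, and 11 is the cautious end.

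**The case for a change.** The strongest case for a change is that the V3.0 set is a stated reason for over-powering the study, so its membership and size should be fixed in advance. Definition by V3.0 baseline criteria, a version label for PP, and either a floor of 29 recruits (24/0.85 = 28.2) or a statement that the 80% is conditional would take a few sentences. Section 21.1.2 also shows that sites had enrolled chronic wounds against the six-week criterion already in force, so screening alone is not proof against error.

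Part of this stands. The set is not listed in Section 10.2, PP carries no version label, and the margin is only one or two subjects if all ten V2.0 enrollees are excluded. No enrolment minimum exists beyond ten acute and ten chronic wounds.

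The rest is weaker. The past misfits were recruited before V3.0 took effect, and the ten-outside case already removes every V2.0 subject counted, so citing them as a further risk counts them twice. Size and exudate are listed as a new criterion, so those earlier recruits do not show that V3.0 criteria will be breached. Under V3.0, exudate and duration failures should be stopped at enrolment by Section 7.6, and undersized wounds are replaced. Further V2.0 enrolment after 19 June 2019 is possible, but under a baseline-criteria definition such a subject still counts if the wound qualifies. In a V3.0 protocol, the eligibility criteria cited for PP most naturally mean that document's own Sections 7.2 and 7.3.

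**Conclusion.** No change to the plan follows. This is missing detail that analysts would fill sensibly. The operative wording in Section 11 is compliance with V3.0, which can be applied at baseline to every subject, and Section 10 leaves further specification to the SAP. No separate SAP text is in the documents, so whether it already supplies the definition cannot be judged.

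The power claim is sound on the plan's figures: 82.1% at 25 evaluable, and 80.4% on the stricter count of 24. A recruitment floor would enrol more patients to guard against a shortfall the plan does not show, and calling the 80% conditional would alter no result. The primary mITT analysis keeps its definition and its power (92.4% at 34 evaluable) however the V3.0 set is drawn.

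This rests on a 3 cm² mean and 5 cm² SD, loss near 15%, and no more than about 11 subjects outside the set. The documents do not give the final number outside. At 13 or more, with loss at the full 15%, this secondary set would fall below 80%, without touching the primary result.

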2. SYNOPSIS

| | |
|------------------------|--|
| Title of Study: | A Prospective, Multi-center, Post-Market Clinical Follow-Up Study to Evaluate the Safety and Effectiveness of ALLEVYN Gentle Border |
| Study Design: | 
 • Prospective • Multi-center • Single-arm |
| Study Type: | Observational Study |
| Study Product: | ALLEVYN Gentle border is a triple layer foam dressing consisting of a highly absorbent hydrocellular foam pad held between a perforated wound contact layer (WCL) which is coated with a soft silicone gel adhesive and a highly permeable outer top film. |
| Comparison Group: | No comparison groups. |
| Study Purpose: | PMCF study to assess clinical performance and safety of ALLEVYN Gentle Border with new wound contact layer to support performance claims. |
| Primary Objective: | To demonstrate clinical performance of ALLEVYN Gentle Border as measured by reduction in the size of the wound area (cm ²) over 4 week treatment period in patients with chronic and acute; full-thickness, partial thickness or shallow granulating, exuding wounds including pressure ulcers, leg ulcers, diabetic foot ulcers and dehisced surgical wounds. |
| Secondary Objective: | To generate safety and performance related data of ALLEVYN Gentle Border in patients with chronic and acute wounds. |
| Other Objective: | None |
| Statistical Rationale: | It is assumed that the actual reduction in the mean wound area from baseline to 28 days is 3cm ² with a standard deviation of 5cm ² . Assuming this data holds true it can be calculated that 26 subjects would provide 83% power to show a statistically significant reduction in the mean wound area from baseline to 28 days. Accounting for the protocol modifications outlined in Section 21, it is recommended to increase the total patient recruitment target to 35 subjects, providing 93% power. Allowing for a 15% lost to follow up rate, 40 subjects will be recruited into this study. |

CONFIDENTIAL AND PROPRIETARY

This document contains information that is confidential and proprietary to Smith & Nephew PLC and Smith & Nephew, Inc. and is intended for use only by Smith & Nephew and its manufacturer. It shall not be reproduced or copied in whole or in part, nor shall the contents be disclosed by any means without prior written permission from Smith & Nephew, nor shall anyone make any use of it that is contrary to the expressed or implied wishes of Smith & Nephew.

| | |
|--|---|

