10.1 GENERAL

Smith & Nephew's Global Biostatistics group will conduct the statistical analysis for this study. Unless otherwise stated, all significance tests and hypothesis testing will be two-sided, performed at the 5% significance level. Resulting p-values will be quoted and 95% two-sided confidence intervals will be generated where appropriate.

Where data summaries are specified, categorical and ordinal variables will be summarized with frequencies and percentages. Continuous variables will be summarized with the following summary statistics: number of observations, mean, median, standard deviation, minimum and maximum values. All analyses will be performed in SAS 9.4 (or later).

The handling of missing data will be detailed in the SAP.

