| 11. Sample Size Justification | To calculate sample size for this study it is assumed that the actual reduction in the mean wound area from baseline to 28 days when using the dressing is 3cm ² with a standard deviation of 5cm ² , this is in line with previous results seen in CE/046/ALF and allowing for marginal differences between study dressings. Assuming this data holds true it can be calculated that 26 subjects would provide 83% power to show a statistically significant reduction in the mean wound area from baseline to 28 days. Allowing for a 15% lost to follow up rate, 30 subjects will be recruited into this study. | The sample size determination for this study was based on a previous study (CE/046/ALF) demonstrating an absolute mean reduction in wound area from baseline to 28 days of 3cm ² with a standard deviation of 5cm ² , in a range of moderate to highly exuding wound types. In order to show a statistically significant reduction in the mean wound area for this study, it was calculated that 26 subjects would achieve 83% power. Unfortunately, several subjects were recruited into the current study with wounds smaller than 3cm ² , little to no exudate or chronic wounds of less than 6 weeks duration, meaning these wounds are not comparable to the previous study in terms of healing challenge. As a result, protocol modifications have been made to ensure a minimum wound size is included in the inclusion criteria as well as provide an opportunity to re-emphasise the challenging nature of wounds we are seeking to recruit with regards to level of exudate. With this |

CONFIDENTIAL AND PROPRIETARY

This document contains information that is confidential and proprietary to Smith & Nephew PLC and Smith & Nephew, Inc. and is intended for use only by Smith & Nephew and its manufacturer. It shall not be reproduced or copied in whole or in part, nor shall the contents be disclosed by any means without prior written permission from Smith & Nephew, nor shall anyone make any use of it that is contrary to the expressed or implied wishes of Smith & Nephew.

| | |
|--|---|
| Study Protocol—Device |  |
| A Prospective, Multi-center, Post-Market Clinical Follow-Up Study to Evaluate the Safety and Effectiveness of ALLEVYN Gentle Border | Number: ALLEV.PMCF.2017.13 |
| | Version: 3.0 |
| | Date: 21 JUN 2019 |
| | Page: Page 72 of 90 |

| | | |
|-----------------------|---|--|

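### Recruiting 40 with 15% loss leaves 34 completers, one short of the 35 to which the plan attaches 93% power (92.4% at 34)

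*Combined protocol and SAP*

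**What the plan says.** Section 11 takes its planning values from a previous study "demonstrating an absolute mean reduction in wound area from baseline to 28 days of 3cm² with a standard deviation of 5cm²". From these, "it was calculated that 26 subjects would achieve 83% power". After the Version 3.0 changes to the eligibility criteria, the number is raised, and "35 subjects would provide 93% power" on the same assumptions. The section closes: "Allowing for a 15% lost to follow up rate as used previously, 40 subjects will be recruited into this study".

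The Statistical Rationale in the synopsis runs the same way. It recommends to "increase the total patient recruitment target to 35 subjects, providing 93% power", and then goes to 40 for a 15% loss. Both places call 35 a recruitment target, but since the next step inflates it for loss, 35 can only be the number meant to remain after loss.

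Section 10.1 sets the error rate: "all significance tests and hypothesis testing will be two-sided, performed at the 5% significance level". Neither place gives the formula that takes 35 to 40.

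**The concern.** A loss allowance exists so that the number remaining after loss equals the number that was powered. Here it does not: taking 15% off 40 gives less than 35. The sentence justifying the sample size therefore claims slightly more power than the recruitment figure delivers on the plan's own loss rate. What is at stake is the internal consistency of Section 11, which any reader can check in one line. The study's ability to detect its assumed effect is not at stake.

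**Working it through.** **Inputs.** Mean reduction 3 cm² and SD 5 cm² (Section 11), so the standardised effect is 3/5 = 0.6. Two-sided 5% level (Section 10.1). Single arm (Sections 6.1.2 and 8.1), so a one-sample test on the change from baseline. Loss 15%, recruitment 40 (Section 11, synopsis).

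**Step 1: reproduce the plan's power.** Power is the probability that a noncentral t variable with n − 1 degrees of freedom and noncentrality 0.6 × √n falls beyond the two-sided 5% critical values of t.

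| n | Noncentrality 0.6√n | Power, two-sided t | Plan states |
|---|---|---|---|
| 26 | 3.06 | 83.6% | 83% |
| 34 | 3.50 | 92.4% | – |
| 35 | 3.55 | 93.2% | 93% |

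Section 11 does not name the test, but the two-sided t is the closest match. For n = 26 and n = 35, the normal approximation gives 86.4% and 94.4%, and the one-sided t gives 90.8% and 96.7%. Under the two-sided t, 35 is the smallest n that reaches 93%.

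**Step 2: apply the stated loss.** 40 × (1 − 0.15) = 34.0 completers, one below 35. Power falls from 93.16% to 92.44%, a difference of 0.7 points.

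**Step 3: what would keep 35.** 35 / (1 − 0.15) = 41.18, so 42 recruits (42 × 0.85 = 35.7; 41 × 0.85 = 34.85 is just short). Equivalently, 40 recruits leave 35 only if loss is 1 − 35/40 = 12.5%.

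**Step 4: how 40 may have arisen.** Section 11 says the allowance is the one used before. The superseded Version 2.0 text, shown in Section 21.1.4, went from 26 to 30: "Allowing for a 15% lost to follow up rate, 30 subjects will be recruited into this study". It is used here only to infer the method; its difference from the current text is not an error.

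| Target | × 1.15 | ÷ 0.85 | Recruited |
|---|---|---|---|
| 26 | 29.9 | 30.6, so 31 | 30 |
| 35 | 40.25 | 41.2, so 42 | 40 |

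Multiplying by 1.15 and rounding to the nearest whole number gives both recruited figures. Dividing by 0.85 and rounding up gives neither.

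**Step 5: the Version 3.0 population.** Section 11 aims for more than 80% power among subjects who comply with Version 3.0. Assume that all 10 subjects enrolled under Version 2.0 are excluded and that the other 30 recruits comply. Then 30 × 0.85 = 25.5 completers, with power 82.1% at 25 and 83.6% at 26. Power stays above 80% down to 24 completers (80.4%).

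**The case against.** Four points can be made for the plan.

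- **The cause is not documented.** A reader might infer that the plan demonstrably used the wrong inflation formula. The documents do not support that. No formula is printed, 40.25 rounded up would be 41, and 40 could simply be a round number. The pattern in step 4 makes multiplication likely, no more. This stands, but the shortfall does not depend on the cause.
- **34 is not the size of the primary analysis.** A reader might infer that only 34 subjects would be analysed. Section 10.2 bases the primary analysis on the mITT population, which requires a single assessment after baseline. Section 10.4.1 takes the day-28 estimate from a repeated measures model across visits. A subject lost after day 7, 14 or 21 therefore stays in the model. This stands: 34 is the expected number completing day 28, and the analysed number equals it only if every lost subject leaves before any post-baseline assessment.
- **93% is not a design requirement.** A reader might infer that the study is underpowered or must enrol more. Section 11 chose 35 to obtain wounds comparable with the previous study and reports 93% as the result. Its only explicit power goal is the one checked in step 5, which is met on the assumptions given there. This stands.
- **The size is trivial, and 15% is itself only a planning guess.** This is true and sets the severity. It does not make 40 less 15% equal 35, which is what the text implies.

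**Conclusion.** Wrong as written, and minor: a nice-to-have correction. With the plan's own 15% loss, 40 recruits leave 34 subjects completing day 28, against the 35 to which 93% power is attached. The size is one completer (two recruits) and 0.7 power points, 92.4% instead of 93.2%.

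This rests on the planning values in Section 11, on a two-sided one-sample t-test (inferred because it reproduces both stated powers), and on reading the 15% as loss before day 28. The t-test stands in for the planned repeated measures model, as it evidently does in the plan's own figure. Multiplication in place of division is the probable explanation, not an established one. Nothing in the design, the analysis or the Version 3.0 power goal is overturned.

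**What to change.** Keep 40 and restate the closing sentence in Section 11 and in the synopsis along these lines: *40 recruited, about 34 expected to complete day-28 follow-up after 15% loss, giving about 92% power under the same assumptions.* The word *complete* is preferable to *evaluable*, which would clash with the mITT definition in Section 10.2.

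The cost is one sentence in two places and a slightly less favourable power figure. Recruitment, sites and timelines do not change, and no extra enrolment is needed. The alternative, recruiting 42 to keep the 93% statement, would add two subjects for 0.7 points and is not worth it.
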